9 STUDY PROCEDURES AND OUTCOME MEASURES

9.1 Outcome measures

9.1.1 *Primary variables*

- Liver fatty infiltration, measured by a MRI technique of fat liver quantification (Ideal IQ**).
- Visceral fat, measured by the area in squared centimeters at the level of the 3rd vertebrae, using MRI technique.

9.1.2 *Secondary variable*

- Liver stiffness detected by MR Elastography
- Adrenal gland linear measurement
- Body weight
- Salivary cortisol levels

9.1.3 *End points*

- Reduction of fat infiltration into the liver between the baseline visit and 2 months (or end of the ketosis stage) and between the baseline visit and the control visit at month 6 of treatment.
- Visceral fat reduction between the baseline visit and 2 months (or end of the ketosis stage) and between the baseline visit and the control visit at month 6 of treatment.
- Correlation between degree of liver fat infiltration and liver stiffness
- Correlation between adrenal gland size and BMI, visceral fat and liver steatosis.
- Correlation between salivary cortisol levels and BMI, visceral fat and liver steatosis.
- Weight loss between the baseline visit and 2 months (or end of the ketosis stage) and between the baseline visit and the control visit at month 6 of treatment.

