9.2 Study procedures

9.2.1 *Follow-up of patients*

The patient follow-up will be 6 months. The patients will be visited monthly and data will be recorded on 4 occasions: pre-inclusion, baseline visit, final visit Active stage (end of ketosis) and visit at month 6.

Patients will be included after verifying the inclusion and exclusion criteria and after obtaining the signed informed consent.

Screening visit (day -15). In this visit, the patient's medical history will be assessed and a complete blood test will be required to verify the inclusion/exclusion criteria: complete blood count (red blood cells, leukocytes, neutrophils, hematocrit, hemoglobin), fasting blood glucose, Hb1c, insulinemia, lipid profile (total cholesterol, c-HDL, c-LDL, triglycerides), kidney function (serum creatinine, creatinine clearance, glomerular filtration), nitrogen balance (urea, uric acid), thyroid profile (TSH, T4) and ionogram (Na, K, Cl, Ca, Mg)

The pre-inclusion blood test will also include liver function tests as the first screening of hepatic steatosis:

- GOT
- GPT
- Gamma-GT
- Bilirubin
- Albumin
- Prothrombin time
- Ferritin
- Alkaline phosphatase.

In addition, the patients will be informed about the study through the patient information sheet (Attachment 1) and they will be provided with an informed consent (Attachment 2).

At the baseline visit (day 0). The results of the additional tests (blood tests) will be verified to complete the inclusion/exclusion criteria.

Liver function data will be reviewed. Patients with one or more of the following conditions will be considered as suspicious of hepatic steatosis:

- GPT/GOT ratio over 1
- Gamma-GT and alkaline phosphatase increased twice to three times the normal levels
- High ferritin
- Normal bilirubin and albumin in the presence of any of the above changes

The informed consent will be signed and randomized. The corresponding diet will be scheduled depending on the treatment group (VLCK diet group or control group) and the physical exercise program. Patient demographics (sex, age, weight, height, comorbidities and medication) will be recorded. Anthropometric data (weight, BMI, waist circumference) will be recorded. Fat infiltration into liver and visceral fat will be scanned by MRI and hepatic stiffness will be assessed by MR Elastography. The salivary cortisol levels will also be tested.

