Control visit at month 2 or at the end of the ketogenic stage: For patients in the VLCK diet group, as soon as the patient loses 80% of the excess weight or within 2 months of treatment, just before moving to phase 3, the patient will undergo a new control. In the case of the control group, this visit will take place at month 2 of the hypocaloric diet.

The patient will undergo a new MRI and MR Elastography. The salivary cortisol levels will also be tested. Anthropometric data are recorded, the patient undergoes a complete blood test including liver function (GOT, GPT, GammaGT, bilirubin, albumin, prothrombin time, ferritin, alkaline phosphatase) and the potential occurrence of adverse effects will be recorded.

Visit at month 6 At month 6 of the study, a new control will be performed, evaluating hepatic steatosis and visceral fat using MRI and liver stiffness using MR Elastography. The salivary cortisol levels will also be tested. A complete blood test including liver function (GOT, GPT, GammaGT, bilirubin, albumin, prothrombin time, ferritin, alkaline phosphatase) will be required and the anthropometric data, the treatment phase, the blood test results and the potential occurrence of adverse effects will be recorded.

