9.2.2 Flow chart

	Pre-study	Onset	Visit at month 2 (end of ketosis)	Visit at month 6 (Final visit)
Review of inclusion and exclusion criteria.	X	X		
General blood test with liver function	X		X	X
Patient information	X			
Informed consent		X		
Comorbidities and medication		X	X	X
Anthropometric data (weight, BMI, WC)	X	X	X	X
MRI + MR Elastography		X	X	X
Salivary cortisol test		X	X	X
Adverse reactions			X	X
Drop outs and end of study			X	X

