13 PRACTICAL CONSIDERATIONS

13.1 Workplan

The investigators will be in charge of recruiting patients. Once the patients have confirmed their willingness to participate in the study, the investigator should verify if they meet the inclusion/exclusion criteria of this study. If they are eligible, they will be requested the additional tests (blood test with liver function) and will be informed on every issue of the study through the Patient Information Sheet (Attachment 1).

At the baseline visit, once the complementary tests have been reviewed and verified to meet inclusion criteria, the physician must confirm that the patient agrees to participate in the study and obtain the patient's signature of the Informed Consent (Attachment 2). Upon signing, the investigator will verify the assigned group according to the randomization list.

At this baseline visit, the physician should request MRI and MR Elastography to assess the degree of hepatic steatosis, the amount of visceral fat and liver stiffness. The physician will also perform the first salivary cortisol test on the patient. Also, he should record the clinical data requested in the Data Collection Notebook and schedule the treatment.

During the weight loss treatment, patients in the study group will be monitored by the investigator fortnightly during the protein diet (Ketogenic Active Stage), although at these additional visits no data are expected to be collected for the study. Upon completion of the first two months of follow-up, the study group will end the ketogenic stage and from that moment on, the patients will be controlled outside the center by dietitians specialized in the Pronokal® Method. Patients in the control group (hypocaloric diet) will undergo controls at the center monthly, although data will only be recorded in the visits arranged in this protocol (screening, baseline, month2 and month 6).

At the moment the patient completes the two months of follow-up, the data requested in the DCN will be recorded, the salivary cortisol test will be performed and an MRI and a MR Elastography will be requested.

The investigator, apart from monthly visits or any additional visits deemed necessary, will have an appointment with the patient at month 6 of treatment for a new clinical assessment, will record the anthropometric data, and request a Control MRI and MR Elastography.

At the end of the 6-month follow-up, the study will be completed.

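### Two conflicting rules time the second measurement for VLCK patients who reach 80% of excess weight lost before month 2; one makes timing response-dependent in that arm only

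*Combined protocol and SAP*

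**What the plan says.** **VLCK arm, event-driven rule.** Section 9.2.1 schedules the second control "as soon as the patient loses 80% of the excess weight or within 2 months of treatment, just before moving to phase 3". The phase rules in section 8.1 agree with this: a patient moves through the phases by share of excess weight lost, and the last ketogenic phase runs to 80%. Section 8.1 adds that patients leave the ketogenic stage within 2 months even if 80% is not reached, so month 2 acts as a cap.

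**VLCK arm, fixed rule.** Section 13.1 states: "Upon completion of the first two months of follow-up, the study group will end the ketogenic stage". On measurement it says: "At the moment the patient completes the two months of follow-up, the data requested in the DCN will be recorded", with the cortisol test, MRI and elastography at that same point. Section 8.1 also contains a sentence giving the active stage a fixed length of 2 months.

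**Control arm.** Section 9.2.1: "In the case of the control group, this visit will take place at month 2 of the hypocaloric diet".

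**Labels that leave it open.** Section 9.1.3 defines the reductions in liver fat and visceral fat, and weight loss, as changes "between the baseline visit and 2 months (or end of the ketosis stage" and again to month 6. Section 9.2.1 lists the last two recording occasions as "final visit Active stage (end of ketosis) and visit at month 6". The flow chart in 9.2.2 heads the column "Visit at month 2 (end of ketosis". Section 7.7 describes the control MRI as coming after ketosis has ended, whereas 9.2.1 puts it just before the change of phase.

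**Analysis.** Section 10.2 compares changes between visits and between groups. It gives no visit window and no adjustment for time since baseline.

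**The concern.** A between-arm comparison of change from baseline needs both arms measured at the same elapsed time, or an analysis that allows for the difference. Under the 9.2.1 rule, a VLCK patient who loses weight quickly is scanned on a day set by that patient's own response, while every control is scanned at month 2. Both primary variables (liver fat and visceral fat) and weight are measured at this visit.

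The difference between arms at this visit would then mix the effect of diet with a difference in time on diet, and the second part would depend on the outcome process itself. Randomization does not protect against this, because the timing is determined after allocation and in one arm only. Under the 13.1 rule the problem does not arise. The protocol does not say which rule governs.

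**Working it through.** There is no planned figure to reproduce: section 7.5 gives 20 per group without an effect size or standard deviation. The check is a comparison of the text, followed by an illustration of where the trigger might fall.

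**Step 1. Same patient, two rules**

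| Patient | Under 9.2.1 | Under 13.1 |
|---|---|---|
| VLCK, reaches 80% before month 2 | scanned when 80% is reached | scanned on completing two months |
| VLCK, does not reach 80% before month 2 | scanned at about month 2 | scanned on completing two months |
| Control | month 2 | month 2 |

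Only the first row differs. The end-of-ketosis wording in 9.1.3, 9.2.1 and 9.2.2 takes its date from whichever rule ends the stage, so it cannot decide between them.

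**Step 2. Where the trigger might fall (illustration only)**

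The documents do not quantify excess weight. Assume it means weight above a reference BMI R. For a patient with BMI B, the trigger as a share of body weight is

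T = 0.8 × (B − R) / B

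| B | R = 27 | R = 25 | R = 23 |
|---|---|---|---|
| 30 | 0.8 × 3/30 = 8.0% | 0.8 × 5/30 = 13.3% | 0.8 × 7/30 = 18.7% |
| 32 | 0.8 × 5/32 = 12.5% | 0.8 × 7/32 = 17.5% | 0.8 × 9/32 = 22.5% |
| 35 | 0.8 × 8/35 = 18.3% | 0.8 × 10/35 = 22.9% | 0.8 × 12/35 = 27.4% |
| 40 | 0.8 × 13/40 = 26.0% | 0.8 × 15/40 = 30.0% | 0.8 × 17/40 = 34.0% |

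The three values of R are assumptions. BMI 30 is the eligibility floor in section 7.2.

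**Step 3. Comparison with the protocol's own background figure**

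Section 4 cites a loss of more than 10% of initial weight at 2 months in 96% of patients on this method. T equals 10% where 0.8 × (B − R) = 0.1 × B, that is, B = 8R/7. This gives B = 30.9 for R = 27, 28.6 for R = 25 and 26.3 for R = 23. Among eligible patients, the trigger is therefore below 10% only for R = 27 and BMI 30 to 30.9.

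The cited 10% is a threshold that most patients exceeded, not a mean, so it does not rule out early triggers above that range. At BMI 32 the trigger is 12.5% with R = 27 and 17.5% with R = 25. By BMI 35 it is at least 18.3% under all three references. Early triggers are plausible mainly near BMI 30-32 and less so as BMI rises. The documents give no BMI distribution and no full distribution of two-month loss, so no count of affected patients follows.

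**The case against.** The strongest case on the other side is that this is a wording inconsistency in an exploratory pilot, affecting an unknown and possibly small group, while month 6, an equally listed time point for both primary variables, is sound. Scanning just before the change of phase is also a coherent choice, and 9.1.3 names the end of ketosis in the endpoint. On this view it would be enough to state one rule and report scan day.

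Much of this stands. The subset is limited, month 6 is unaffected, and an end-of-ketosis scan answers a legitimate question within the VLCK arm. However, choosing the event-driven rule and reporting scan day would remove the contradiction and leave the one-arm timing difference in the comparison. Pilot status does not help much either, because with 20 patients per arm each differently timed scan is 5% of the arm (1/20).

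A reader might infer more than the documents support:

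- **Three competing timings.** End of ketosis is a label, not a separate rule. There are two rules.
- **Sites applying different definitions of the trigger.** Section 8.1 refers to excess weight, a target and a goal, but these may be one quantity under several names. What is shown is that the quantity is not defined.
- **Scan timing that cannot be traced.** Section 13.1 says "patients in the study group will be monitored by the investigator fortnightly during the protein diet" and expects no study data from those visits. The Data Collection Notebook is not among the documents, so whether it captures scan dates is unknown.

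**Conclusion.** The point holds in limited form. The protocol has two incompatible rules for the second measurement in VLCK patients who reach 80% of excess weight lost before month 2. If the 9.2.1 rule is followed, the first between-arm comparison of both primary variables and of weight has response-dependent timing in the VLCK arm only, with no allowance in the analysis. VLCK patients who do not reach 80% early, and the month-6 comparison, are not affected.

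No bias in a particular direction should be inferred. A patient scanned early has had less time on the diet, but is also selected for rapid loss, and 9.2.1 ties the trigger to a change of phase, after which loss need not continue at the same rate. The number affected, the size and the direction cannot be derived. The figures of 8.0-18.7% at BMI 30 and 18.3-27.4% at BMI 35 rest on assumed reference BMIs of 27 to 23. The reading that early triggers are plausible mainly near BMI 30-32 also assumes that the background figure carries over to this population. Confidence is high for the conflict in wording and for the asymmetry under 9.2.1. This should be fixed, but it does not undermine the trial as a whole.

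**What to change.** - For the between-arm comparison, take the second MRI, elastography, cortisol and weight in one common month-2 window counted from diet start, with the same stated tolerance in days in both arms, whatever weight has been lost. Section 13.1 already sets measurement at two months.
- Align the visit-timing wording in sections 7.7, 9.1.3, 9.2.1, 9.2.2 and 13.1.
- Record the actual scan day and report it by arm.
- Separately, the sponsor must reconcile the statements in 8.1, 9.2.1 and 13.1 on when the ketogenic stage ends. This review takes no position on that rule.

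The cost is protocol wording and one recorded date per scan, with no extra scans. The downside is that, for a patient who leaves ketosis early, the month-2 scan is not an end-of-ketosis scan. The end-of-ketosis alternative in 9.1.3 would then go unmeasured for that patient unless a scan were added, and any end-of-ketosis results would be a description within the VLCK arm.

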9.2.2 Flow chart

	Pre-study	Onset	Visit at month 2 (end of ketosis)	Visit at month 6 (Final visit)
Review of inclusion and exclusion criteria.	X	X		
General blood test with liver function	X		X	X
Patient information	X			
Informed consent		X		
Comorbidities and medication		X	X	X
Anthropometric data (weight, BMI, WC)	X	X	X	X
MRI + MR Elastography		X	X	X
Salivary cortisol test		X	X	X
Adverse reactions			X	X
Drop outs and end of study			X	X

10 STATISTICAL ANALYSIS

10.1 Descriptive statistics

A descriptive statistics will include all variables collected in the Data Collection Notebook. Frequency tables will include the nominal variables and measures of central tendency and dispersion for the continuous variables. 95% confidence intervals (95% CI) will be estimated for the latter.

10.2 Analysis of objectives

For the analysis of the primary objective and the secondary objectives, the differences between visits and between groups will be studied for the changes in the ratio between liver fat and the degree of steatosis (measured by MRI), changes in the degree of liver stiffness, changes in cortisol levels in saliva, weight changes, BMI and waist circumference, and changes in the amount of visceral fat among visits. The qualitative variables will be compared using Fisher's exact test, and the quantitative variables will be compared by means of the Student's t test for paired data. If the conditions to apply the Student's t test are not met, we will use the non-parametric Mann-Whitney U test. In the case of comparing paired data, we will use the tests described above, in their version for comparing this type of data.

The Pearson correlation coefficient or Spearman's correlation coefficient if the application conditions are not met will be used to study the following: the association between reduction of hepatic steatosis and weight loss and loss of visceral fat; the association between hepatic steatosis and liver stiffness; and the association between adrenal gland size and salivary cortisol levels with weight changes, BMI, hepatic steatosis and visceral fat.

For all tests, the significance level will be set at $p < 0.05$.

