1.12 Outcome Measures

- Body weight loss
- Visceral fat (measured by the area in squared centimeters at the level of the 3rd vertebrae, using MRI technique)
- Porcentaje de contenido graso del hígado
- Liver stiffness using MR Elastography
- Linear measurements of the adrenal glands
- Salivary cortisol levels

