Liver biopsy is the gold standard in diagnosing NAFLD and the most accurate tool for grading fibrosis. However, is invasive and carries the risk of complications (3). Also, histological examination of biopsy samples is subject to sampling error due to histological heterogeneity. Scoring is semi-quantitative, limiting its ability to detect modest changes, and scoring results vary between reports precluding direct comparisons. Various imaging techniques are proposed for liver fat quantification. Liver fat fraction (FF) can be calculated using fat and water MRI signal intensities in chemical-shift images (in-phase [IP] and out of phase [OP] sequences). Typically, the fatty liver shows increase in signal intensity (SI) on IP images and shows diffuse signal drop in OP image. The fat fraction can then be determined by calculating the loss of SI in OP images as compared to IP images. From congruent sets of IP and OP images,

acquired within the same breath-hold sequence, the fat fraction can be calculated pixel-wise, and misregistration errors can be avoided (4). MRI multiecho method estimates T2* from six different echo times (TE). This method resulted in improved diagnostic specificity compared with that of the triple-echo method which caused systematic underestimation at high FFs (1). New noninvasive methods including MR elastography have been developed for o distinguish necroinflammation and mild fibrosis from simple steatosis (4). Given that the spectrum of fatty liver disease ranges from simple steatosis, through stages of liver cell injury (steatohepatitis), to fibrosis, and eventually to cirrhosis, it is appropriate to ask whether hepatic stiffness as a biomarker can be used to identify the presence of liver cell injury prior to the onset of fibrosis.

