One of the leading extra-hepatic causes of liver steatosis is metabolic syndrome (MS). Although, multiple definitions of MS exists; the essential components of MS include insulin resistance, increased levels of stress hormones, such as cortisol, and visceral obesity. In the obese population, the hallmarks of a metabolic syndrome are highly prevalent, being peripheral insulin resistance and increase levels of stress hormones the leading causes of organ injury. In such individuals higher levels of cortisol are expected, secondary to an over activated hypothalamic-pituitary-adrenal (HPA) (13, 14). A linear correlation between adrenal gland volume and metabolic syndrome has been demonstrated, with increased adrenal volume in patients under a metabolic syndrome status. However, once these patients are engaged on a treatment regime, leading to weight loss and diminished insulin resistance, the increase in adrenal volume tends to be reversible. Adrenal volume measurements can be achieved using cross-sectional imaging and semi-automated softwares. In clinical practice, adrenal gland dimensions are generally assessed using limb linear measurements on multidetector row computed tomography or magnetic resonance imaging (15,16).

We conducted a prospective longitudinal clinical study to correlate the effects of a very low-calorie-ketogenic diet (PRONOKAL method*), body weight loss and visceral fat reduction, with liver fat fraction, using a new MRI model of fat liver quantification (Ideal IQ**). Additionally, the degree of liver fat and its evolution, during the diet program, will be correlated with liver stiffness using MR Elastography. Adrenal gland measurements will also be made using the linear technique described by Carsin-Vu A. (16) to address its correlation with weight loss, visceral fat and liver steatosis.

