5 STUDY OBJECTIVES

5.1 Primary aim

- To evaluate the effects of body weight loss after a very low-calorie-ketogenic diet (Pronokal Method®) versus low calorie diet, on visceral fat reduction, liver fatty infiltration, using a new MRI technique of fat liver quantification (Ideal IQ**).

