8 TREATMENT DESCRIPTION

8.1 Weight Loss Program: PronoKal® Method

All patients in the study group will undergo the same standardized weight loss program (PronoKal® Method) with progressive diet based on commercial high-biological-value protein preparations, dietary supplements, physical exercise plan and emotional support, structured in 3 stages: active stage, food re-education stage and maintenance stage

80% of target weight loss			20% of target weight loss		Long-term maintenance of weight loss
Multidisciplinary team (Dietary counseling/physical activity/psychological support)					
Weight Loss Moment					My New Lifestyle Moment
Step 1	Step 2	Step 3	Step 4	Step 5	
Low-fat ketogenic diet (very low-calorie-ketogenic diet) 600-730 kcal/day			Low calorie diet (800-1500 kcal/day)		Controlled diet adapted
Supplementation Vitamins, trace elements OMEGA BALANCE: 700 DHA/500 EPA			Supplementation Vitamins, trace elements DHA VITA: 500 DHA/100 EPA		DHA VITA: 500 DHA/100 EPA

a) Treatment schedule

Active stage: The diet will consist of a protein diet, ie a very low-calorie ketogenic diet (VLCK diet) (between 650 and 730 kcal/day) based on PronoKal® commercial preparations and low-glycemic-index vegetables. Patients will start with 5 commercial

preparations a day. Two of them will be replaced progressively by natural proteins (meat or fish). This active stage will be maintained for 2 months.

- Phase 1: Protein diet of 600 kcal/ day (with 5 PronoKal® products and low-glycemic-index vegetables) + Nutritional supplements (vitamins and trace elements) + Cardiovascular physical exercise + Emotional support.
- Phase 2a: Protein diet of 680 kcal/day (with 4 PronoKal® products, a high-protein food [meat or fish] and low-glycemic-index vegetables) + Nutritional supplements (vitamins and trace elements) + Cardiovascular physical exercise + Emotional support.+ Soporte emocional.
- Phase 2b: Protein diet of 780 kcal / day (with 3 PronoKal® products, two high-protein foods [meat or fish] and low-glycemic-index vegetables) + Nutritional supplements (vitamins and trace elements) + Cardiovascular physical exercise + Emotional support.

Patients will remain in Phase 1 until they have lost 40% of the excess weight or the target weight to be lost. Subsequently, they go on to Phase 2a until they have lost 60% of the excess weight and then to Phase 2b until they have lost 80% of the excess weight.

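### Does Section 10.2 test an undefined ratio instead of the primary liver fat variable?

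*Combined protocol and SAP*

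**What the plan says.** Section 10.2 opens by covering the primary and secondary objectives together and lists the changes to be compared between visits and between groups. The liver fat item in that list is "changes in the ratio between liver fat and the degree of steatosis (measured by MRI"). Liver stiffness, salivary cortisol, weight, BMI, waist circumference and visceral fat follow as separate items.

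Other sections describe the same measure as follows:

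- Section 5.1 (primary aim) concerns the effect of the two diets "on visceral fat reduction, liver fatty infiltration, using a new MRI technique of fat liver quantification (Ideal IQ").
- Section 9.1.1 (primary variables): "Liver fatty infiltration, measured by a MRI technique of fat liver quantification (Ideal IQ").
- Section 9.1.3 (endpoints): "Reduction of fat infiltration into the liver between the baseline visit and 2 months (or end of the ketosis stage"), and likewise from baseline to month 6.
- Section 1.12 (outcome measures), left in Spanish: "Porcentaje de contenido graso del hígado", that is, the percentage fat content of the liver.
- Section 4 (rationale) sets out to correlate diet, weight loss and visceral fat reduction "with liver fat fraction, using a new MRI model of fat liver quantification (Ideal IQ").

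The second paragraph of Section 10.2, on correlations, refers to hepatic steatosis and its reduction without any ratio.

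**The concern.** The list in Section 10.2 is the only place where the plan says which quantities will be tested for the primary objective. The liver item there is worded as one quantity divided by another. Neither the ratio nor a steatosis grade is defined in any section, and plain liver fat is not listed beside it. Section 10.1 covers liver fat only descriptively, and the correlation paragraph does not compare the diets.

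Liver fat is one of only two primary variables. If the phrase were applied as written, the stated analysis would not test the endpoint of Section 9.1.3. The trial is also open-label (Section 6.4), so a primary outcome that had to be defined at the analysis stage could be chosen with the results in view.

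**Working it through.** The plan gives no figure to reproduce here. Section 7.5 states 20 patients per group without an effect size, standard deviation or power, and the question does not depend on that number. The check is to take each possible meaning of the phrase and see whether the rest of the protocol supports it.

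**Reading 1: liver fat percentage or fraction, badly translated.**

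- Section 1.12 gives the outcome as a percentage, and Section 4 calls it a fraction.
- The word ratio has a natural source, because a fat fraction is itself a ratio. Section 4 says: "Liver fat fraction (FF) can be calculated using fat and water MRI signal intensities in chemical-shift images".
- The English text was not fully cleaned. Besides the Spanish line in Section 1.12, Section 8.1 has "Emotional support.+ Soporte emocional", where the same item appears in both languages.
- The word degree need not mean a grade. Section 10.2 uses it for liver stiffness, a measured quantity, and Section 13.1 uses it for the hepatic steatosis that MRI assesses.

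On this reading the tested quantity is the variable of Section 9.1.1, and the difference from the intended analysis is 0.

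**Reading 2: numerator and denominator are the same MRI measure.** Write F for MRI liver fat. The ratio is F / F = 1 at every visit, so its change is 1 − 1 = 0 for every patient on either diet. Nothing could be tested. An analyst would see this before running anything and go back to Section 9.1.1.

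**Reading 3: the denominator is a steatosis grade.** The documents contain no grade, cut-off or coding, so this reading can be explored only with assumed values. Take one assumed patient whose liver fat falls from 20% to 8%.

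- Direct relative change: (8 − 20) / 20 = −60%.
- Grades 0–3 with assumed cut-offs 5/15/25: 20/2 = 10 falls to 8/1 = 8, which is −20%.
- Grades 0–3 with assumed cut-offs 5/10/20 and 20% placed in the higher grade: 20/3 = 6.67 rises to 8/1 = 8, which is +20%.
- The same cut-offs with 20% placed in the lower grade: 20/2 = 10 falls to 8/1 = 8, which is −20%.

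The ratio would also be undefined at grade 0. The apparent reversal of sign comes only from an example value sitting exactly on an assumed cut-off. These figures show that a grade-based ratio would be a poor outcome. They do not show that this trial planned one, and power figures built on such gradings would have no more support in the documents.

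**Comparison.** Reading 1 agrees with Sections 1.12, 4, 5.1, 9.1.1, 9.1.3 and 13.1 and with the second paragraph of Section 10.2. Reading 2 makes the primary comparison empty. Reading 3 needs a scale that the protocol never mentions.

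**The case for a change.** The strongest argument for a change is that an analysis section should state its own primary variable and not leave it to be inferred. Liver fat goes by several names across the protocol, but only Section 10.2 words it as a ratio of two quantities, and it does so where the test is specified. Correcting it would take one line and no new data, visits or patients. That the intent can be recovered is, on this view, a reason to make an easy correction. The translation slip is also an inference: leftover Spanish shows that the translation was imperfect, not what this phrase meant.

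Part of this stands. The phrase is undefined, it does concern a primary variable, and only the sponsor can confirm what was meant. The worry about a choice made after seeing the data does not stand. Sections 5.1, 9.1.1 and 9.1.3 already fix the measure, the MRI method, the direction of change and the time points. An analyst who substituted a ratio would depart from the declared primary variable, and any reader of Section 9.1 could see it. The varied names elsewhere show no conflict with one another, so harmonising them would be copy-editing.

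**Conclusion.** The wording of Section 10.2 is a real but clerical slip, and it does not call for a change to the plan. The conclusion rests on one assumption: that the phrase stands for MRI liver fat as a percentage or fraction, which is the only reading consistent with the rest of the protocol. On it, the numerical effect is zero for the liver fat comparison between groups and between visits. The visceral fat analysis is unaffected on any reading. No sample size, significance level or visit depends on the phrase, and correcting it would alter no result. The judgement would change only if the sponsor stated that a graded ratio was truly intended, and nothing in the documents suggests that.
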